#### [1.4/ Abbreviations and Acronyms](#)

COVID-19: Corona virus disease-2019

CHILL: Cooling to Help Injured Lungs

ALI: Acute lung injury

TH: Therapeutic hypothermia

NMB: Neuromuscular blockade

ARDS: Acute respiratory distress syndrome

SOFA: Sequential organ failure assessment

VFDs: Ventilator-free days

P/F: Ratio of partial pressure of oxygen:fractional index of inhaled oxygen

OSI: Oxygen saturation index

ECMO: Extracorporeal membrane oxygenation

FRH: Febrile-range hyperthermia

MICU: Medical intensive care unit

UMMC: University of Maryland Medical Center

CRRT: Continuous renal replacement therapy

SAE: Serious adverse event

HSCTI: Human subject clinical trial information

LAR: Legally authorized representative

CRF: case report forms

CCU: Cardiac care unit

CCRU: Critical care receiving unit

CVP: Central venous pressure

CCC: Clinical Coordinating Center

DCC: Data Coordinating Center

CSPCC: Cooperative Studies Program Coordinating Center (in [name])

##### 2.1.1.2 Clinical Operations Core (CC)

The Clinical Operations Core (CC) will be headed by Drs. [name] and [name]. The CC is responsible for oversight of all aspects of trial enrollment and recruitment, from feasibility assessment, to planning, tracking and, if necessary, improving protocols. The CC is also responsible for supervising the biomarker analysis.

###### 2.1.1.2.1 Specific Responsibilities of the CC:

1. Collect and maintain all regulatory documents (curricula vitae, CITI GCP certifications, CITI human subjects research, clinical lab CLIA certification and normal ranges).
2. Provide training to all clinical personnel regarding GCP, screening and clinical protocols.
3. Develop and maintain all study protocols and standard operating procedures regarding patient screening and clinical protocols and collecting and handling research samples.
4. Maintain real-time tracking and correction of clinical protocol noncompliance
5. Establish and manage the IRB approval
6. Report adverse events to IRB, DC, and DSMB
7. Maintain continuous monitoring of data quality
8. Monitor human subject protection
9. Manage the CHILL-pilot record in Clinicaltrials.gov
10. Monitor enrollment for meeting timing and budgetary milestones
11. Maintain oversight of biomarker core
12. Manage supply of Nimbex provided as a study drug gift by Abbvie Pharmaceutical

#### 2.1.2 Data Management

##### 2.1.2.1 Data Management and Analysis Core (DC)

The Data Management and Analysis Core (DC) will be jointly run by [name], and [name], CM, MPH. The DC is responsible for oversight of randomization and data management, data quality, statistical analysis, and providing data summaries to external groups.

###### 2.1.2.1.1 Specific Responsibilities of the DC:

1. Maintain oversight of the Randomization and Data Management Core, including the computer-based CHILL treatment assignment tool and Screening/enrollment tool.

2. Provide instruction and training to clinical personnel regarding randomization and data management processes, procedures, and metrics.
3. Perform database back-up and post-study database lock.

### 2.1.3 Laboratories

#### 2.1.3.1 *The Biomarker Core (BC)*

The Biomarker Core will be directed by [name]

##### 2.1.3.1.1 Biomarker Core Components

The Core has three components:

- 1 sample storage
- 2 University of Maryland Cytokine Core Laboratory
- 3 [name] basic research laboratory.

##### 2.1.3.1.2 Biomarker Core Procedures

1. Samples will be stored in a remotely monitored -80°C freezer with liquid CO2 back-up located in the University of Maryland Baltimore Health Science Facility-II in ancillary space adjacent to [name] basic research laboratory (Rm S116).
2. Labeled EDTA-anticoagulated blood samples from all participating ICUs will be transported on ice directly to [name] laboratory within 30 minutes of collection and processed as described in the Sample and Processing section. The [name] laboratory is adjacent to UMMC
3. Samples will be batched for assays to be performed every 4-6 months. [name], will hand-carry one aliquot in labeled cryotubes per blood draw in marked freezer boxes on ice to the Cytokine Core Laboratory located on the seventh floor of the adjacent Bressler Research Building.
4. Samples will be received by [name], Supervisor of the Cytokine Core Laboratory, who will place the samples in the Cytokine Core Laboratory remotely-monitored, liquid-CO2-backed-up -80°C freezer until she performs the planned immunologic assays.
5. All assays will be performed in the Cytokine Core Laboratory using in-house ELISAs (IL-1 $\beta$ , IL-6, IL-8, IL-18, and sTNFR1) or purchased ELISA kits (sRAGE, SP-D, sICAM-1, MMP8).
6. [name] is the Director of the University of Maryland Cytokine Core Laboratory and has weekly meetings with [name] to review throughput and quality of all projects in the Cytokine Core Laboratory. The progress of the CHILL-pilot analysis will be discussed as part of these weekly meetings.
7. [name] will analyze all CHILL-pilot biomarker data for reproducibility and monitor performance of all biomarker assays by inspecting the standard curve, monitoring within-assay coefficient of variance between replicate measurements, and between-assay coefficient of variance based on pre-aliquoted internal controls to be included on each assay plate.

## 2.2/ Administration and Governance

### 2.2.1 Committees

#### 2.2.1.1 CHILL Pilot Executive Committee (CEC)

The CEC membership will include Drs. [name], [name], [name], and Brown. The CEC will meet bi-weekly to monitor progress with study planning milestones during the preparation phase and enrollment, randomization, retention, and data quality milestones during the enrollment and randomization phase. The CEC will review suggestions for protocol amendments from all CHILL-pilot personnel and make final decisions about modifying protocols. [name] will prepare reports for Data Safety Monitoring (DSM) meetings with input from [name].

##### 2.2.1.1.1 Responsibilities of the CEC:

1. The CEC will meet bi-weekly to monitor progress with enrollment, randomization, retention, and data quality milestones and re-evaluate and revise as needed all study protocols.
2. The CEC will review suggestions for protocol amendments from all CHILL-pilot personnel and make final decisions about modifying protocols.
3. [name] will prepare reports for DSM meetings with input from [name].
4. Serious/Reportable Adverse Event (SAE/RAE) Adjudication and Reporting: The following is an initial plan for adverse event (AE) reporting (the plan will be revised by the CHILL leadership with input from CHILL personnel and the CHILL Data Safety monitor, [name], based on experience with the ongoing study). Serious Adverse Events are defined as any deaths, life-threatening events, or events that prolong hospitalization that occur within the first three study days (which includes the period of cooling and rewarming in the Therapeutic Hypothermia arm). All SAEs will be reviewed by [name] based on information provided by [name]. [name] will report the SAE, including his assessment of relatedness to study procedures, to the UMB IRB and the Data and Safety Monitor, [name] within 48 hours of discovery. Reportable AEs (RAEs) that do not meet the threshold for SAEs are defined as any clinically important untoward medical occurrence in the first study week which is different from what is expected in the clinical course of a patient with ARDS. All other AEs will be tabulated without case-by-case review unless a difference between treatment groups calls for review of a group of cases. [name] will submit monthly tabular reports of all SAEs/RAEs to [name] and will submit tabular summaries of all AEs to [name] every 6 months. The AE summary will be included in the bi-annual review by [name].
5. Ongoing Scientific Review: CEC members and any other interested CHILL-pilot personnel may bring new information with potential impact on study protocols and analysis to the attention of the entire CEC. The topic will be added to the CEC meeting agenda and background information distributed with enough lead time to allow a productive discussion.
6. Processing Requests for Sample Sharing: [name] will provide to the CEC all information about sample sharing requests and information about sample availability

and status of the CHILL-pilot biomarker analysis to inform decisions by the CEC about the priority of sample sharing requests.

7. Publication Preparation: The entire CEC membership will participate in manuscript writing. Drs. [name] and [name] will take the lead with the first paper about study design. Drs. [name] and Brown will take the lead the manuscript reporting the main study results. [name] will update the Clinicaltrials.gov record.
8. Oversight of Biomarker Core: The research biomarker analysis will be performed by the CHILL-pilot Biomarker Core with oversight by [name].

#### 2.2.1.2 Data Management Core Committee

Oversight for the Randomization and Data Management Core will reside within the DC. One or members of the clinical team will transcribe data from the patient study binder to an Excel form that summarizes the salient data for analysis to be performed by Drs. [name] and [name]. [name] will oversee generation of random assignments into the computer-based CHILL assignment tool, which records date and time, and name of investigator performing randomization.

##### 2.2.1.2.1 Responsibilities of the Data Management Core Committee

1. During the self-funded phase [name] will provide the following two monthly recruitment reports:
  - (1) a screening/recruitment report that presents the counts of patients screened, enrolled, and randomized without treatment assignment information, for distribution to and discussion in the CEC, and
  - (2) a list of patient ID (PID) numbers and letter codes (Letcode) sorted by date of randomization with treatment stratum and treatment assignment for each patient. Drs. [name] and Brown will check the list against the randomization schedules prepared by [name], against the monthly screening and randomization table and use it to ensure congruence with clinical site documents and in preparation of DSM reports with tabulated data.

#### 2.2.2 Funding Agency

The initial phase of this pilot RCT is self-funded. The larger Phase IIb trial is funded by DoD with enrollment to begin Fall, 2020

#### 2.2.3 Data Safety Monitoring (DSM)

##### 2.2.3.1 DSM composition

###### 2.2.3.1.1 For CHILL-pilot: self-funded phase

The Data Safety Monitor for the self-funded phase is [name], a Pulmonary and Critical Care Physician who is not directly related with the study, is familiar with the management of ARDS and the conduct of clinical trials, and who has been approved by the University of Maryland Internal Review Board.

### 2.2.3.2 DSM procedures

The Data Analysis and Management Core (DC) will be responsible for managing Data Safety Monitoring, including preparing reports for bi-annual review by [name]. The following is an initial plan for adverse event (AE) reporting, which will be modified and finalized based on discussions with the DSMB:

1. Clinical site staff will be responsible for recording all AEs on the appropriate CRF.
2. Any deaths, life-threatening events, or events that occur within the first three study days, including NMB, cooling and rewarming, and unexpected SAEs occurring in the first study week will be reviewed by [name] based on information provided by [name].
3. [name] will report the SAE, including his assessment of relatedness to study procedures, to the University of Maryland Baltimore IRB and [name] within 48 hours of discovery.
4. All other AEs will be tabulated without case-by-case review unless a difference between treatment groups calls for review of a group of cases.
5. [name] will submit monthly tabular reports of all SAEs and other RAEs to [name] and will submit tabular summaries of all AEs to [name] every 6 months.
6. Since this is a small pilot study, there are no plans for an interim analysis and early termination based on futility or proven benefit.

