
We have been approved for funding by Department of Defense (DoD) to support for a 4-year multicenter RCT of TH+NMB for 48h vs. standard of care with contract to be completed June 1, 2020 and with enrollment to begin in Fall of 2020. This study was designed prior to the onset of COVID-19, which is now the most common cause of ARDS and will likely continue to be in the Fall, 2020 and perhaps beyond. Therefore, it is important to decide whether patients with COVID-19 ARDS should be enrolled in our CHILL trial. Therefore, we will conduct a 20-patient pilot safety and feasibility trial of our CHILL TH+NMB treatment vs. control in COVID-19 patients with ARDS who meet the inclusion/exclusion criteria of our DoD-funded trial. The major objective of the proposed pilot trial is to determine whether it is safe and feasible to include patients with COVID-19 ARDS in our Phase IIb CHILL RCT of TH+NMB vs. control in patients with moderate to severe ARDS.

The pilot will be conducted at the University of Maryland Medical Center. To facilitate randomization within the inclusion window, we will consent and enroll based on partial fulfillment of randomization criteria and randomize once all criteria are met. Patients will be

eligible for enrollment when they have been diagnosed with COVID-19 by PCR, and have met all Berlin criteria for moderate to severe ARDS within the 48h inclusion window except the P/F ratio  $\leq 200$  but will not be randomized until P/F ratio (measured or imputed based on SpO2) is  $\leq 200$  (while on  $\geq 8$  cm H2O PEEP and  $\geq 0.6$  FiO2). We plan to randomize a total 20 patients over 4 months to hypothermia (core temperature 34°-35°C for 48h) plus NMB or usual temperature management. The primary outcome measures will be effectiveness of cooling in achieving and maintaining the target temperature and safety measures. Secondary outcomes will include 28-day ventilator-free days (VFDs), 28-day ICU-free days, oxygen saturation index (OSI), driving pressure, Sequential Organ Failure Assessment (SOFA) score, 60-day and 90-day survival, 90-day functional assessment, cognitive assessment at ICU and hospital discharge, and biomarkers of inflammation and lung injury. Since the nature of the intervention precludes blinding, all treatment and clinical decision making related to study outcomes will be protocolized and compliance with study protocols will be monitored.

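### If the 6-month clock starts at first enrolment, the first all-AE summary and bi-annual review fall about 2 months after all 20 patients have been randomised and treated

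*Protocol*

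**What the plan says.** The Synopsis (Protocol 1.1) sets the pace: "We plan to randomize a total 20 patients over 4 months". Section 8 gives a 54 h treatment period after randomisation, and the schedule in section 6 marks AE monitoring out to day 90.

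Safety information travels by three routes, set out in 2.2.1.1.1 item 4 and 2.2.3.2 and largely repeated in section 12:

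- **Expedited.** SAEs are reported "to the UMB IRB and the Data and Safety Monitor, [name] within 48 hours of discovery" (2.2.1.1.1).
- **Monthly.** The responsible investigator "will submit monthly tabular reports of all SAEs and other RAEs to" a recipient whose name is masked (2.2.3.2 item 5).
- **Six-monthly.** The responsible investigator "will submit tabular summaries of all AEs to [name] every 6 months" (2.2.3.2 item 5). "The AE summary will be included in the bi-annual review by" a person whose name is masked, evidently the Data Safety Monitor (2.2.1.1.1 item 4). The introduction to 2.2.3.2 gives the data core the matching duty, "including preparing reports for bi-annual review by" that person.

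For events outside the first two routes, 2.2.3.2 item 4 says: "All other AEs will be tabulated without case-by-case review unless a difference between treatment groups calls for review of a group of cases".

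The scope of the fast routes is stated most narrowly in 2.2.1.1.1. There SAEs are deaths, life-threatening events or events prolonging hospitalisation "that occur within the first three study days". Reportable AEs (RAEs) are clinically important events in the first study week that differ from the expected course of ARDS.

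Item 6 of 2.2.3.2 rules out an interim analysis for futility or benefit, and the SAP plans no interim analysis at all.

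**The concern.** The 6-month interval is longer than the planned enrolment period. The rule for AEs below the SAE/RAE threshold depends on someone seeing a difference between arms, but the only stated delivery of a table of all AEs is six-monthly. As scheduled, that trigger has nothing to act on while patients are still being randomised and cooled.

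Safety is a primary outcome of this pilot, and its result is meant to decide whether COVID-19 patients can safely enter the Phase IIb trial. Section 11 lists infection, fluid and chemical disturbance, hyperglycaemia and reduced clotting as risks of cooling. When such events are non-serious and judged expected in ARDS, or are non-serious and arise after the first week, they can fall outside the 48-hour and monthly routes. An imbalance in them is something a small safety pilot should be able to notice while it is running. There is no evident backstop: the criteria for ending hypothermia early in section 8 apply to individual patients, and the monitoring sections state no arm-level safety rule.

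**Working it through.** The plan gives no figure of its own on this point, so the check is timeline arithmetic.

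**Inputs.** 20 patients over 4 months (1.1); 54 h treatment period (section 8); AE monitoring to day 90 (section 6); all-AE summary every 6 months (2.2.1.1.1, 2.2.3.2, section 12); bi-annual review (2.2.1.1.1, 2.2.3.2), read as every 6 months because the AE summary feeds it.

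**Assumptions.** Uniform accrual; clock starting at first enrolment (not stated in the documents); a month of 30.4375 days.

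**Planned schedule**

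- Accrual rate: 20 / 4 = 5 per month. Patient *i* is randomised at month 0.2 × *i*, the last at month 4.0.
- Last 54 h period ends: 4 + (54/24)/30.4375 = 4 + 0.07 = month 4.07.
- Last day 28: 4 + 28/30.4375 = month 4.92.
- Last day 90: 4 + 90/30.4375 = month 6.96.
- Gap from last randomisation to first review: 6 − 4 = 2 months.
- At month 6, 20 of 20 are randomised, 20 of 20 are past the 54 h period and none is still within 28 days.
- Still in 90-day follow-up at month 6: those randomised after month 6 − 2.96 = 3.04, which are patients 16 to 20, so 5 of 20.
- Monthly SAE/RAE tables at months 1, 2, 3 and 4 fall after about 5, 10, 15 and 20 randomisations.

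**Sensitivity to slower accrual** (clock at first enrolment). Patients remain to be randomised at month 6 only if the rate is below 20/6 = 3.3 per month.

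| Accrual period (months) | Randomised by month 6 | Still to be randomised |
|---|---|---|
| 4, 5 or 6 | 20 | 0 |
| 8 | 15 | 5 |
| 12 | 10 | 10 |

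**Sensitivity to an earlier clock** (accrual 5 per month). If the clock starts *s* months before first enrolment, the review falls at enrolment month 6 − *s*, with max(0, 20 − 5 × (6 − *s*)) patients still to be randomised.

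| *s* (months) | Review at enrolment month | Still to be randomised |
|---|---|---|
| 0, 1 or 2 | 6, 5 or 4 | 0 |
| 3 | 3 | 5 |
| 4 | 2 | 10 |
| 5 | 1 | 15 |

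**Scope of the fast routes.** The passages do not agree on which SAEs are covered:

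- 2.2.1.1.1 item 4 limits SAEs to the first three study days.
- 2.2.3.2 item 2 adds unexpected SAEs in the first study week to the case review.
- Section 12 (Serious) defines seriousness with no time limit.
- Section 12 (Reporting requirements) puts deaths and life-threatening events temporally related to study procedures, and unexpected SAEs, into the 48-hour process with no day limit.

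Later SAEs are therefore covered or not depending on which passage is followed. Non-serious events that are expected in ARDS, or that arise after week 1, are outside the fast routes on every reading.

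**The case against.** The best defence is that the trial has timely safety oversight without the six-monthly table. SAEs go out within 48 hours and SAE/RAE tables monthly. RAEs span the first study week, which contains the whole 54 h treatment period. Section 12 also requires new or increased risk to be reported to the IRB within 5 business days, with no time window. The trial is open-label and single-centre, study staff see patients daily through day 7 (3.5), the daily forms ask about bradycardia, bleeding and new pneumonia, and the executive committee meets every two weeks. Section 2.2.3.2 item 4 gives no frequency for tabulation, only item 5 for submission, and a monthly list with treatment assignments already supports safety reports (2.2.1.2.1).

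Most of this stands, and it rules out two stronger readings. A reader might infer that the late review can protect no patient. That goes too far, because about 5 of 20 would still be under AE follow-up at month 6. A reader might also infer that any excess of later or non-serious events would first be seen after enrolment. The documents do not establish that for later serious events, given section 12, or for imbalances that staff notice informally.

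Informal awareness is nevertheless not a scheduled comparison of all AEs by arm put before an independent monitor. Nor does it help that 2.2.3.2 calls the plan initial and open to revision: the 6-month interval is stated in three places and is the rule until changed.

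**Conclusion.** The concern holds in a limited form. On planned accrual, with the clock starting at first enrolment, the first all-AE summary and bi-annual review come about 2 months after the last randomisation. All 20 patients would by then have completed the treatment period, so neither could alter any patient's enrolment or study treatment. The review rule for other AEs therefore has no scheduled between-arm table behind it during enrolment. The clear gap is AEs below the SAE/RAE threshold; whether it extends to later SAEs depends on which definition governs.

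The size depends on the unstated clock start and on accrual. A clock starting 3 to 5 months before enrolment would leave 5 to 15 patients still to be randomised at the review, and accrual over 8 to 12 months would leave 5 to 10. Nothing in the documents indicates an early clock, and under slow accrual half or more of the patients would still be randomised before the first look. This is a scheduling weakness in a trial with safety as a primary outcome, and does not mean that safety oversight is absent.

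**What to change.** Three changes to the text:

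1. In 2.2.1.1.1 item 4, 2.2.3.2 item 5 and the reporting requirements of section 12, replace the 6-month interval with an all-AE table by arm added to the existing monthly SAE/RAE report. State that it goes to the Data Safety Monitor by role, since the public text masks who receives the monthly report.
2. In 2.2.1.1.1 and 2.2.3.2, tie the monitor's periodic review to enrolment instead of the calendar, for example at about the half-way count of 10 randomised patients. The review then falls during enrolment whatever the accrual rate or start date.
3. Reconcile the SAE time window across 2.2.1.1.1 item 4, 2.2.3.2 item 2 and section 12, so that it is clear which later SAEs enter the 48-hour and monthly routes.

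The tables should be descriptive. At 10 patients randomised 1:1 there are about 5 per arm, too few for a formal test to be the trigger. Because they contain no efficacy comparison, they leave the SAP's test of ventilator-free days and its alpha untouched. The cost is a few extra tables from the data core and short reviews by the existing monitor.

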## 2.3/ Roles and Responsibilities

### 2.3.1 Multiple Principal Investigators (MPI)

#### 2.3.1.1 Contact MPI

The contact MPI for the CHILL-pilot is [name]. Responsibilities include:

1. [name] will direct the CHILL-pilot Administration Group
2. [name] will chair the CHILL-pilot Executive Committee (CEC).
3. [name] will interact with [name] regarding distribution of study resources, including quarterly payments to UMMC for study-related costs and to Axio Research LLC should an R24 grant be awarded.
4. [name] will direct the Biomarker Core and ensure proper handling of research samples and timely, high quality biomarker analysis.

